**Background (*Literature review*):**

Tacrolimus is an immunosuppressant which acts by inhibition of calcineurin. It's typically used as a first line drug to prevent allograft rejection in renal transplant patients (1). With pharmacokinetic variability between patients and a narrow therapeutic range, therapeutic drug monitoring (TDM) is essential to support graft survival. Low levels of tacrolimus risk organ rejection, whilst toxic levels risk nephrotoxicity and other adverse effects including neurotoxicity, electrolyte disturbances and hyperglycaemia (2). Clinical guidelines suggest target tacrolimus ranges, but levels are determined by renal clinicians and are patient specific, depending on individual circumstances, as well as the time since transplantation (3).

Renal transplant patients require lifelong monitoring of immunosuppressant levels and renal function to assess graft kidney stability. Renal function is monitored by measuring serum creatinine and urine protein excretion, levels of which determine the need to perform a biopsy if graft dysfunction is suspected (3). Creatinine is the product of creatine phosphate catabolism in muscle. Its endogenous production at a constant rate and clearance by glomerular filtration makes it a useful marker of graft function, with increasing levels indicating a reduced glomerular filtration rate and thus some element of renal disease (4). Creatinine is measured enzymatically on the Roche platform, as part of a urea and electrolyte panel.

The Renal department is currently managing just under 1000 patients with a functioning kidney transplant, with this number increasing annually. There are 80-100 transplants per year and a current waitlist of just under 300 patients. Following successful transplantation, every patient requires lifelong monitoring of transplant function. This is not only a long-term commitment for these patients, but also the renal department in providing the aftercare. Current practice for post-transplant monitoring involves regular venepuncture to collect a venous blood sample for tacrolimus measurement and a 'dialysis profile' (urea and electrolytes, bicarbonate, CRP). Clinical guidelines recommend monitoring tacrolimus levels by trough sample 3 times a week initially. Frequency decreases over time to every 4-6 weeks at 6-12 months and then every 3-6 months at 12 months post-transplant, unless adjustments are made to the dosage which warrants more frequent

monitoring. Serum creatinine should be measured at each clinic visit, as well as urine dipstick analysis for urine protein (3). Thus, the frequency of biochemical monitoring depends on patient circumstances, but once a steady state is achieved, the monitoring window increases.

The COVID-19 pandemic put considerable strain on patient care, with limited access to healthcare settings (including phlebotomy services) due to increased infection control measures. Transplant patients are already immunocompromised and often have comorbidities, so it is important to minimise unnecessary exposure to high-risk environments, including hospital settings. When presenting with COVID-19, solid organ transplant patients have an increased 30-day mortality compared to non-transplant patients, and they are also more likely to require mechanical ventilation and critical care (5). Furthermore, COVID-19 has been noted as a causative factor in graft rejection and subsequent loss (6). The risks associated with COVID-19 infection are applicable to various other disease groups, including patients undergoing cancer treatment (7). This highlights a requirement to protect these vulnerable groups in the hope of a more favourable patient outcome. To overcome some of the challenges imposed by COVID-19 and alleviate the associated risks for renal transplant patients, virtual appointments (by telephone or video consultation) were utilised. This enabled patients to attend their appointment anywhere, providing greater flexibility to both the patient and clinician. However, there is little benefit to these virtual appointments if the patient is still required to attend a healthcare setting for blood sample collection. Hence, alternative approaches to blood sample collection were explored.

A promising microsampling device has been growing in popularity. Neoteryx (Torrance, CA 90501, USA) has developed Mitra® devices with VAMS® (volumetric absorptive microsampling) technology. Patients collect a capillary blood sample by finger prick and send it to the laboratory for testing. Studies have shown results correlate well with those obtained from a venous blood sample collected by venepuncture (8, 9). There has been a positive bias noted for capillary tacrolimus concentrations, but this could be overcome by establishing new target ranges for patients (10). This method of sample collection is already being utilised by 2 Trusts within the UK to support transplant monitoring in paediatric patients.

The technology will be trialled in a small group of adult renal transplant patients with the intention to implement the blood collection strategy into routine clinical practice. This has the potential to significantly improve the patient pathway for renal transplant patients and reduce the economic burden. Reduced demand on blood clinics will increase availability for patients requiring renal transplant work-up, but also improve access to these services for patients from other departments. Remote blood collection, in addition to continued utilisation of virtual consultations frees up clinic availability for pre-transplant patients, whilst also reducing administration requirements for transplant nurses, who can better direct their time towards the patient. This strategy should empower the patient, thereby improving compliance and making care more efficient, all whilst greatly minimizing patient risk by removing the requirement for patients to regularly attend a hospital setting for their lifelong aftercare.

#### **Research Question:**

To compare tacrolimus and creatinine concentrations in venous samples collected by venepuncture and capillary samples collected using volumetric absorptive microsampling technology.

#### **Objectives and Specific Aims:**

- To develop and validate an LC-MS/MS method for tacrolimus and creatinine measurement in adult renal transplant patients.

- To compare tacrolimus and creatinine concentrations in venous samples collected by venepuncture and capillary samples collected using Mitra® devices.
- To implement home blood sample collection into routine clinical practice for renal transplant patients.
- To publish the study findings to encourage uptake of remote blood sample collection using VAMS® technology.

#### **Rationale and Significance of Study:**

The main advantage of this collection method is that it allows the remote collection of a blood sample. This reduces patient attendance at blood clinics and resultant strains on phlebotomy staff and clinics, eliminates administration requirements for transplant nurses and saves both the patient and the NHS time and money. Of most importance is the great flexibility and convenience this collection device offers, as patients can collect samples at anytime and anywhere, providing greater freedom compared to current procedures.

Patient adherence to immunosuppressants is a key factor in potential graft rejection, with lack of immunosuppression leading to graft loss, even years after transplantation (12). Due to the increased flexibility offered by the Mitra® device, it is anticipated that this collection method will improve patient compliance with TDM. Better timed sample collection is also expected (ie. a 'true' trough sample) as patients are not subject to blood clinic operating hours. Consequently, potentially more frequent and better-timed sample collections will be more clinically useful.

Importantly for patient management, is the ability to calculate AUC (area under the curve). This is not currently possible with current protocols as regular samples would be required which inconveniences the patient. AUC targeted therapeutic monitoring of tacrolimus may be more clinically informative than current pre-dose tacrolimus measurements and be a better indicator of immunosuppressant efficacy (13).

It is also worth noting the current issues encountered with venepuncture for venous blood collection. Increased patient anxiety occurs because of needle phobia (although uncommon) and if the patient is difficult to bleed. The latter of which can result in lengthy appointments whilst the required samples are obtained. In comparison, capillary blood sampling is minimally invasive, and a much smaller volume of blood is required (particularly useful for the elderly). However, a well-known issue associated with capillary blood is the volumetric haematocrit bias and poor blood spot quality, resulting in non-homogenous samples and inaccurate results (14). This issue is alleviated using Mitra® devices because a defined blood volume is collected.

VAMS® technology has been trialled in other TDM settings including cardiovascular (15). It is anticipated that this study will highlight the good correlation of results obtained from the different sample collection methods and ease of use of the collection device. Thereby supporting the implementation of Mitra® devices for blood collection into routine clinical practice, not just for TDM but also for other analytes such as HbA1c. Additionally, there is the potential to automate sample extraction, optimising laboratory workflow.

#### **Research Design**

##### **Recruitment of Participants**

A minimum of 50 adult renal transplant patients (>18 years old) taking tacrolimus as part of their immunosuppressant regime will be recruited from December 2022 when attending their routine outpatient follow up appointment. A patient information sheet will be distributed to the patients.

Written consent will be obtained from all participants.

## **Methodology**

### **Sample collection**

Patients attending blood clinic for routine venepuncture will also have a finger prick and 10 $\mu$ l blood will be collected using the Mitra® device (Neoteryx), according to manufacturer's instructions. The usual venous EDTA and serum samples will be collected by venepuncture by trained phlebotomists/nurses. Tacrolimus and creatinine are measured in venous blood samples (whole blood and serum, respectively) as part of routine patient care therefore these will be processed as normal, and results reported. The paired capillary samples collected using the Mitra® device will be batched and run when appropriate on the LC-MS/MS. Mitra® devices will be stored at -20°C prior to analysis. Any incorrectly filled Mitra® devices (over or under filled) which would affect sample quality will be rejected.

### **Sample analysis**

Venous EDTA whole blood samples (collected by venepuncture) and capillary whole blood samples (collected by VAMS®) will be analysed for tacrolimus using a validated LC-MS/MS assay in routine clinical use in the lab using the Waters ACQUITY UPLC system and Xevo TQD MS. Additionally, samples from the UK NEQAS immunosuppressants scheme will be analysed as above for tacrolimus. Capillary whole blood samples (collected by VAMS®) and serum samples will be analysed for creatinine using an LC-MS/MS method which will be developed based on a previously published method (11). For the method comparison, serum samples (collected by venepuncture) will be analysed for creatinine using an enzymatic method on the Roche platform. Additionally, samples from the UK NEQAS clinical chemistry scheme will be analysed as above for creatinine. All sample analysis will be performed in an ISO 15189 accredited laboratory.

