### **Sample collection comparison**

To compare results collected by venepuncture and results collected by VAMS® sampling, a minimum of 50 paired patient samples will be analysed for tacrolimus and creatinine by LC/MS-MS. 20 EQA samples from the NEQAS immunosuppressant scheme will be analysed for tacrolimus and 20 EQA samples from the NEQAS clinical chemistry scheme will be analysed for creatinine by LC-MS/MS. To compare creatinine methods (enzymatic and LC-MS/MS), creatinine samples will also be analysed using an enzymatic assay on the Roche platform.

To test the stability of whole blood collected by VAMS®, 5 samples will be stored at varying temperatures for 7, 14 and 21 days. The samples will be stored at -20°C, 4°C, room temperature and

37°C. This will test the effect of temperature extremes which may occur due to postal delivery of the Mitra® devices. The stability of post extraction samples will also be tested by storing the 96 well plate at 4°C post analysis and re-assaying at 24 and 48 hours post extraction. To investigate the effect of different haematocrit concentrations, blood cells and plasma will be mixed 20:80, 40:60, 60:40 and 80:20 to obtain 4 different haematocrit levels (20%, 40%, 60% and 80%).

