#### **Deriving a new reference range**

If the LC-MS/MS tacrolimus and/or creatinine method shows a clinically significant bias compared to current methods, this will be confirmed by obtaining further patient comparison data. If confirmed, the reference range will need to be reviewed and amended accordingly. Any bias identified by Bland-Altman analysis will be used to derive a new reference range for patients being monitoring using blood collected using the Mitra® devices.

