#### **Data Analysis**

Statistical analysis will be performed based on CSLI recommendations and departmental protocols.

Study population characteristics (including patient age, tacrolimus dose, time since transplantation, haematocrit) will be expressed as median (range).

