#### **Sample collection comparison**

All samples will be analysed in duplicate and the results averaged. Passing-Bablok regression and Pearson correlation coefficient will be used to compare and assess correlation of the results of venous and capillary samples. Bland-Altman analysis will assess agreement and determine presence of any bias between the results obtained from venous and capillary sample collection. 95% confidence intervals will be calculated. Statistical analysis will be performed using the Analyse-It add-in for Microsoft Excel.

Stability: Samples will be analysed in duplicate and the results averaged. Means of each group will be

calculated and compared to baseline. Differences of  $\pm 15\%$  will be deemed acceptable.

**Effect of haematocrit concentration:** The 4 samples will be analysed in duplicate and the results averaged. Differences of 15% will be deemed acceptable and this would confirm samples collected using Mitra® devices are unaffected by differing haematocrit concentrations.

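### The creatinine pairs compare capillary whole blood with venous serum, so the difference called collection bias also contains a matrix component that may vary with haematocrit

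*Protocol*

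**What the plan says.** **Matrices.** Under Sample collection, the protocol says that routine venous tacrolimus is measured in whole blood and routine venous creatinine in serum. Under Sample analysis, the tacrolimus comparison is matched: "Venous EDTA whole blood samples (collected by venepuncture) and capillary whole blood samples (collected by VAMS®) will be analysed for tacrolimus". The creatinine comparison is not: "Capillary whole blood samples (collected by VAMS®) and serum samples will be analysed for creatinine using an LC-MS/MS method". Nowhere is creatinine measured in venous whole blood, although venous EDTA blood is drawn.

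**Analysis.** Methodology, Sample collection comparison, treats the two analytes alike: "To compare results collected by venepuncture and results collected by VAMS® sampling, a minimum of 50 paired patient samples will be analysed". Under the same title in Data Analysis, Bland-Altman analysis is to "determine presence of any bias between the results obtained from venous and capillary sample collection".

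**Use of the result.** Deriving a new reference range says: "Any bias identified by Bland-Altman analysis will be used to derive a new reference range for patients" monitored with Mitra devices. This applies once a clinically significant bias has been confirmed in further patient data.

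**Haematocrit.** It enters in two places. One is a laboratory experiment in which "blood cells and plasma will be mixed 20:80, 40:60, 60:40 and 80:20 to obtain 4 different haematocrit levels", with a 15% acceptance limit. The other is a descriptive summary: "Study population characteristics (including patient age, tacrolimus dose, time since transplantation, haematocrit) will be expressed as median (range". The protocol does not relate a patient's haematocrit to that patient's paired difference.

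**The concern.** For tacrolimus, a venous-capillary difference can fairly be read as an effect of site and device. For creatinine, the same calculation also contains the difference between whole blood and serum. If red cells and plasma hold creatinine at different concentrations, that third component depends on how much of the patient's blood is cells, so it is not one number for all patients.

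The fixed tip volume, which Rationale and Significance of Study offers as the answer to haematocrit bias, controls how much blood is taken. It does not control how creatinine divides between cells and plasma within that volume. Passing-Bablok regression can show bias that changes with concentration, but not bias that changes with haematocrit. The enzymatic versus LC-MS/MS comparison concerns the assay.

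The Background describes serum creatinine as a marker of graft function whose level informs the decision to biopsy, and the Objectives aim at routine home sampling. If the matrix effect is material, a patient whose haematocrit changes could show a change in Mitra creatinine while serum creatinine stays the same.

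**Working it through.** The protocol gives no figure for this effect, so there is none to reproduce. The size is illustrated by mass balance.

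**Inputs**
- From the protocol: the two matrices, a minimum of 50 pairs, mixtures at 20, 40, 60 and 80% haematocrit, and the 15% limit.
- Assumed, not in the protocol: R, the ratio of creatinine concentration in cells to that in plasma, at 0.6, 0.7, 0.8 and 1; patient haematocrit from 0.25 to 0.50; average haematocrit 0.38.

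**Step 1: whole blood relative to serum**

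Ratio(H) = (1 − H) + H·R = 1 − H(1 − R)

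**Step 2: error left after one correction set at H = 0.38**

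Residual(H) = Ratio(H) / Ratio(0.38) − 1

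| R | Ratio at 0.25 | Ratio at 0.38 | Ratio at 0.50 | Residual at 0.25 | Residual at 0.50 |
|---|---|---|---|---|---|
| 0.6 | 0.900 | 0.848 | 0.800 | +6.1% | −5.7% |
| 0.8 | 0.950 | 0.924 | 0.900 | +2.8% | −2.6% |
| 1 | 1.000 | 1.000 | 1.000 | 0 | 0 |

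Moving the centre to 0.36 gives +5.1% and −6.5% for R = 0.6, and +2.4% and −3.0% for R = 0.8, so the picture does not depend on the centre chosen.

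**Step 3: would the four-mixture experiment reveal it?**

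Take R = 0.7 and the 40% mixture as reference (the protocol names no reference mixture). The ratios at 20, 40, 60 and 80% are 0.94, 0.88, 0.82 and 0.76.
- 0.94/0.88 − 1 = +6.8%
- 0.82/0.88 − 1 = −6.8%
- 0.76/0.88 − 1 = −13.6%

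All lie within 15%, so the samples would be declared unaffected while whole blood reads 12% below serum at haematocrit 0.40. The experiment has no paired serum and does not say which analyte it covers.

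**Step 4: what 50 pairs can say about the slope**

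Assume a haematocrit SD of 0.05 and an SD of paired percent differences of 5 to 10 points. The standard error of the slope is SD/(0.05 × √49), which is 14.3 to 28.6 points per unit of haematocrit. From Step 1 the true slope is −100(1 − R): −20 at R = 0.8 and −40 at R = 0.6. The power of a two-sided 5% test is then about 28% down to 11% at R = 0.8, and about 78% down to 28% at R = 0.6.

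The 95% half-width of the haematocrit-related error at 0.13 from the centre (0.38 − 0.25) is 2.01 × 14.3 × 0.13 = 3.7 points, rising to 2.01 × 28.6 × 0.13 = 7.5 points. Fifty pairs can bound the error roughly, but a non-significant slope would not show independence from haematocrit.

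**The case against.** **Serum is the right comparator.** Mitra is meant to replace a routine serum measurement, so the total Mitra-serum difference is the quantity needed, and the protocol states both matrices openly. This stands. A reader might infer that the creatinine comparison is invalid, or that serum should be dropped; the documents do not support either. What remains is how the difference is attributed and how it is carried forward.

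**The effect is conditional.** A reader might infer that a haematocrit-dependent error is certain. It is not: R is not in the documents, and the effect vanishes at R = 1. This stands and limits the claim.

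**The size is modest.** Residuals of about 3 to 6% lie below the protocol's 15% haematocrit limit and its 20% precision limit. That bears on priority. But those limits concern laboratory experiments, and the protocol sets none for error in an individual patient's corrected creatinine.

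**Haematocrit is already tested.** At R = 0.6 the 80% mixture would differ from the 40% mixture by −19.0% and fail. At R = 0.7, however, the test passes (Step 3), so it does not close the gap.

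**No constant correction is prescribed.** The range section requires confirmation in further data and then review, and it never says that the correction is constant. That is fair. Even so, the only quantity it names for deriving the range is the Bland-Altman bias, and nothing there lets it vary with haematocrit.

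**A covariate analysis may be in an unseen analysis plan.** It may be. The point therefore rests on what the protocol does fix: a collection label on a mixed-matrix difference, and a range derived from that difference.

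**Conclusion.** The point holds in a limited form. It is certain from the text that the creatinine difference combines site, device and matrix, and that the protocol describes it as collection bias. That the matrix part varies with haematocrit follows only if R differs from 1, which the protocol neither states nor tests in patients. In that case one average correction leaves about +2.8% and −2.6% at haematocrit 0.25 and 0.50 for R = 0.8, and about +6.1% and −5.7% for R = 0.6. These figures rest on the assumed R, an assumed haematocrit range and an assumed average of 0.38.

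The finding is a reason to check before one bias is applied to every Mitra patient. It does not show that Mitra creatinine is unreliable.

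**What to change.** 1. Describe the creatinine comparison as *capillary whole blood versus venous serum*, and keep serum as the comparator.
2. In Data Analysis, Sample collection comparison, regress the paired creatinine percent difference (Mitra minus serum) on the patient's haematocrit. Use the value already listed as a population characteristic, taken as close to the paired draw as available.
3. Report the slope with its 95% CI, expressed as the implied error at the lowest and highest haematocrit observed.
4. State a limit in advance and judge the implied error and its CI against it. Do not decide by whether the CI excludes zero; Step 4 shows how often that rule would miss a real slope.
5. If the limit is not met, do not derive the creatinine range from one constant bias. Make it haematocrit-dependent, or limit the claim to the haematocrit interval that the data support.

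**Cost.** One regression and a change of wording, with no new study samples if a haematocrit value near the draw is available. The protocol does not say when haematocrit is measured, and the routine bloods listed in the Background do not include it, so this needs confirming. The creatinine claim may become narrower, and with about 50 pairs the slope may be imprecise. The regression does not separate collection site from matrix; it shows only whether one correction is adequate across haematocrit.
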